When appropriate, all data analysis will be conducted for the entire study and individually by site. Qualitative data will be comprised of the translated, verbatim transcripts of the in-depth interviews and FGD. Textual data will be managed using the MAXqda10 (VERBI Software, 1989-2012). A codebook for each set of qualitative data will be created, tested for inter-coder reliability, and used to code the transcripts. When appropriate, qualitative data will be used to modify and improve intervention components and guide selection of adaptable components at each site. De-identified quantitative data will be entered into Microsoft Access databases. Range checks, disallowing invalid values, and adaptive double entry, along with regular data audits will ensure the accuracy of the electronic data. Data analysis will be conducted using SAS primarily. Descriptive analysis will be performed for all variables and outliers will be investigated for data errors. A probability of <0.05 will be considered statistically significant for all tests.

Aim 1: Success of program implementation will be assessed as follows:

- a) Program Adoption: Program adoption will be measured by quantifying participation in the program and success in reaching the goals of the lifestyle education program (weight loss, increased physical activity and diet improvements). Participation will be measured by calculating the percentages of total employees agreeing to screening, agreeing to participate in the program, and enrolling in lifestyle classes. Attendance records for study classes and other activities and numbers of diet/activity tracking booklets turned in for review by the health educator will be reviewed to determine percent attendance at each class and at classes overall. Physical activity [in Metabolic Equivalent of Task (METS)/day] will be quantified using the Global Physical Activity Questionnaire (GPAQ).⁹⁴ Diet changes will be quantified through a study-specific food frequency questionnaire, which will include food items that participants are encouraged to eat more or less often, as well as questions on diet-related behaviors (e.g., reading food labels, measuring portion sizes). A healthy diet score will be calculated from the food frequency questionnaire and other diet related questions.^{95,96} Changes in weight, BMI, waist circumference, physical activity, and diet score over time will

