Aim 2: Statistical analysis of intervention impact: A generalizing estimating equations (GEE) framework for clustered data⁹⁷ will be used to assess the statistical significance of any observed intervention effect on the endpoints. For the primary endpoint, the dependent variable will be the indicator for whether the study participant is at two or more cardiometabolic risk factor reduction goals at the end of the 3 year follow-up period, minus the expected probability of this endpoint in the absence of an intervention, to be taken as 21% as observed in the D-CLIP²⁵ control group. An exchangeable working correlation matrix will be used to incorporate the clustering within the 8 work-sites, with a log link and binomial variance specified. The exponentiated point and interval estimates from the intercept of this model will quantify the intervention effect, and the p-value associated with the model's intercept will provide a measure of the statistical significance of the findings. A similar GEE approach will be used to estimate and test the significance of intervention effects on secondary endpoints. For continuous markers, such as systolic blood pressure and HbA_{1c}, the post- to pre- within-participant difference will serve as the dependent variable in a GEE model as above, with the identity link function and the distribution specified as normal. The change scores will be evaluated for outliers, and analysis will be repeated with and without extreme outliers. For the cumulative incidence of diabetes at end of follow-up, participants will be coded as one if they satisfy the diabetes definition at end of follow-up and 0 otherwise. A Cox proportional hazards regression model for the diabetes incidence rate will also be considered, and if dropout or loss to follow-up are non-negligible, causal methods for adjusting for dependent censoring will be applied.¹⁰² A similar approach will be used to assess regression to normoglycemia. We will consider worksite-level covariates in multi-level models to examine how these aspects might affect findings. Additional secondary endpoints will be considered (e.g., changes in being at 1, 2 and 3 CVD/T2DM risk factor goals). Although the study is not powered to detect it unless quite large and although no effect modification is expected, we will assess the presence of effect modification by calculating intervention effect estimates stratified by potential modifiers, such as gender, age, marital status, socio-economic status, and assess the statistical significance of any effect modification observed by calculating a cross-product term between the potential modifier and the intervention, using a robust score test to assess the significance of

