Sample Size Selection: This worksite-clustered before-after design of 8 worksites with at least 250 eligible and enrolled participants per site and no more than 20% loss to follow-up (LTF) after 3 years will have 93% or more power to detect an estimated difference between the percent of participants at 2 or more CHD risk factor goals after 3 years of follow-up, the primary effectiveness endpoint of this trial, of 33% or greater, compared to the comparable D-CLIP²⁵ percentage of 21%. The 20% 3-year LTF rate is likely conservative, as only 9% of D-CLIP participants have been lost to follow-up after a mean of 30 months. Similarly, the D-CLIP comparative percentage of 21% is likely conservative, because the D-CLIP control group also experienced a minimal intervention that included meeting with a physician and a dietician, attending two classes (a lecture on diabetes

prevention through weight loss and diet change, and an exercise class), and receiving handouts reinforcing prevention of T2DM. Thus, compared to a community control receiving none of these services, the D-CLIP group would be expected to have a higher percentage at or exceeding two goals, compared to the community standard. In addition, power in this study is excellent for numerous secondary effectiveness endpoints of considerable interest, including 90% power or more to detect a decrease of 2mmHg or greater in systolic blood pressure ($p=0.10$, IIS), 95% power or more to detect a decrease in HbA_{1c} of 0.14% or greater ($p=0.10$, IIS), and nearly 100% power to detect a reduction in diabetes incidence of 30% or greater among the 2/3 of the study participants with prediabetes at baseline screening, compared to the baseline rate of 0.07/year,¹²⁴ otherwise under the same assumptions as the primary endpoint calculation.

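### The primary GEE puts a log link on the goal indicator minus 0.21, so its intercept p-value does not test P = 21%, its exponentiated interval can never include a zero difference, and it has no solution at an observed 21% or below

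*Combined protocol and SAP*

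**What the plan says.** Under Data Analysis, Aim 2, the dependent variable for the primary endpoint is the indicator of being at two or more risk-factor goals at three years, "minus the expected probability of this endpoint in the absence of an intervention, to be taken as 21" per cent, the figure seen in the D-CLIP control group. An exchangeable working correlation is used to "incorporate the clustering within the 8 work-sites, with a log link and binomial variance specified". On the effect measure: "The exponentiated point and interval estimates from the intercept of this model will quantify the intervention effect". On the test, the p-value for the model's "intercept will provide a measure of the statistical significance of the findings". The opening of Data Analysis sets the threshold: "A probability of <0.05 will be considered statistically significant for all tests".

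For secondary endpoints, "A similar GEE approach will be used to estimate and test the significance of intervention effects on secondary endpoints". Continuous markers use the within-person change "in a GEE model as above, with the identity link function and the distribution specified as normal".

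Sample Size Selection states that the design "will have 93% or more power to detect an estimated difference between the percent of participants at 2 or more CHD risk factor goals", with 33% or greater set against 21%. The null that the trial wants to reject is therefore P = 21%. Neither section mentions an offset, a non-zero null value for the intercept, a variance estimator, a reference distribution for 8 clusters, or a fallback if the model cannot be fitted.

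**The concern.** Subtracting 0.21 from the response and then applying a log link combines two devices that do not belong together. Subtraction goes with an identity link, where a zero intercept means no difference from 21%. A log link goes with an offset of log(0.21), where a zero intercept means a ratio of 1 against 21%. In the combination the plan describes, a zero intercept means neither.

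The trial has no control group, so this one comparison with 21% carries the effectiveness claim. If the stated analysis is followed, the primary p-value answers a question nobody is asking, and the model breaks down when the programme shows no benefit. If it is not followed, the analyst must choose between two repairs with different effect measures and different power, possibly after seeing the data.

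**Working it through.** **Inputs.** From Sample Size Selection: 8 sites × 250 enrolled, 20% loss, so 8 × 200 = 1,600 analysed; target 33%, reference 21%. From Data Analysis: alpha 0.05, taken as two-sided. The intracluster correlation (ICC) is not clearly stated for this endpoint, so 0 to 0.10 is an assumed range.

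**The plan's own power figure.** With n_eff = 1600/(1 + 199 × ICC), one-sample power is Φ[(0.12 − 1.96 × SE0)/SE1], where SE0 = √(0.21 × 0.79/n_eff) and SE1 = √(0.33 × 0.67/n_eff). This gives 99.8% at ICC 0.02, 91.7% at 0.05 and 70.4% at 0.10. An ICC of about 0.047 returns 93% (0.032 to 0.064 across two-sided normal variants; 0.027 with t on 7 df). Without a stated ICC, the 93% can be neither confirmed nor refuted.

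**Algebra of the model as written.** The log link gives E(Y − 0.21) = exp(b0), so exp(b0) = P − 0.21.
- Setting b0 = 0 gives P = 1 + 0.21 = 121%, which is impossible. P = 21% needs exp(b0) = 0, that is b0 = −∞.
- exp(b0) is a risk difference: at 33% it is 0.12 and b0 = log(0.12) = −2.12. Exponentiated limits are always positive, so zero is never inside the interval.
- If the observed proportion is 21% or less, exp(b0) would have to be zero or negative, so no finite b0 exists.

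**Worked values at ICC 0.04.** The design effect is 1 + 199 × 0.04 = 8.96. The literal test is z = log(p − 0.21)/[SE/(p − 0.21)]. The offset test is z = log(p/0.21)/(SE/p).
- Observed 25%: SE = √(0.25 × 0.75 × 8.96/1600) = 0.0324. Literal: −3.219/0.810 = −3.97, p = 0.00007. Offset: 0.174/0.130 = 1.35, p = 0.18 (0.22 with t on 7 df).
- Observed 22%: SE = √(0.22 × 0.78 × 8.96/1600) = 0.0310. Literal: −4.605/3.10 = −1.49, p = 0.14, with an exponentiated interval of 0.00002 to 4.35, although no difference can exceed 1 − 0.21 = 0.79.

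Smallest observed proportion giving p < 0.05:

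| ICC | Literal | Offset, z | Offset, t on 7 df |
|---|---|---|---|
| 0.04 | 22.4% | 26.8% | 27.9% |
| 0.10 | 23.6% | 29.7% | 31.3% |

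**Simulation at a true 21%** (40,000 beta-binomial trials per setting, 8 × 200, ICC 0 to 0.10, between-site sandwich SE):
- no solution in 51–53% of trials;
- p < 0.05 in 60–77% of fitted trials, or 29–37% of all trials;
- interval excludes a zero difference in 100% of fitted trials, with an upper limit above 0.79 in 24–44% of them.

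**Check with fitted exchangeable GEEs.** On a data set with 24.8% observed, the literal fit gave intercept −3.267 (SE 0.567) and the offset fit 0.167 (SE 0.0871), both matching the closed forms. On a data set with 20.4% observed, the literal intercept ran off to about −7 × 10^48 with SE 0, yet the software reported convergence and p = 0.

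**Eight clusters (a separate point).** After the link is repaired, an uncorrected sandwich with a normal reference has type I error 2 × P(t7 > 1.96 × √(7/8)) = 0.109. With t on 7 df, the offset model gives 4.8–5.1% (K−1 correction) or 3.7–4.0% (Mancl-DeRouen). The identity model gives 5.0–6.3% or 3.9–5.3%.

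**The case against.** The strongest reply is that the authors meant a risk ratio against 21%. The log link, binomial variance, exponentiated intercept and intercept test all fit that reading, and an offset of log(0.21) would make them coherent. This is plausible. But the text puts the subtraction in the dependent variable, and Sample Size Selection speaks of a difference, although it may use the word loosely and does not define an effect measure. An identity link on the shifted indicator is also a possible intention, so the text does not settle the choice.

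Second, the failures would be noticed: an absurd intercept, or an interval reaching 4.35. Often they would, so 29–37% should be read as what the stated rule gives, not as a forecast of what would be published. Not every failure is obvious, however. An observed 25% at ICC 0.04 gives a tidy estimate of 0.04 and a very small p-value, and the diverged fit above was flagged as converged.

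Third, the false-positive rate applies at a true 21% exactly, and the plan argues that an untreated group would fall lower. That stands. At a true 18%, literal p < 0.05 occurs in 0–11% of all trials, and at 15% in 0–3%. Non-fitting then rises to 77–100% at 18%, so the primary analysis still gives no answer.

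Fourth, at the planned 33% both models usually reject: for ICC up to 0.04, 100% literal against 97–100% offset with uncorrected z. At ICC 0.10 they part, 97% against 77%.

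Two limits also stand. The one binary secondary endpoint the plan codes explicitly, cumulative diabetes incidence, has nothing subtracted, so inheritance of the fault is conditional. And the literal model was not run in SAS, the plan's main package, which may treat a response of −0.21 or 0.79 under a binomial specification differently.

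**Conclusion.** The primary model is wrong as written and must be corrected before analysis. The three faults (wrong null, an interval that cannot include a zero difference, no solution at 21% or below) follow from algebra and hold at any ICC. The sizes depend on assumptions: 8 × 200 analysed, ICC between 0 and 0.10, a two-sided 0.05 test and, for the error rates, a true proportion of exactly 21%. On those terms about half of null trials cannot be fitted and 29–37% of all null trials give p < 0.05. At ICC 0.04 the literal rule reaches significance from an observed 22.4%, where a test of 21% needs 26.8% or 27.9%. The missing small-sample method is a separate gap that would remain after the link is repaired.

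**What to change.** Choose one model and state its scale, null and variance method in advance.

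- **Option A, risk ratio:** model the 0/1 indicator itself with a log link and a fixed offset log(0.21). Then exp(intercept) = P/0.21, which is 1.571 at 33%, and a zero intercept is exactly P = 21%.
- **Option B, risk difference:** model the indicator minus 0.21 with an identity link and report the intercept without exponentiating. This is a different effect measure, so the choice must be explicit.

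For either, specify a small-sample-corrected sandwich (K−1 or Mancl-DeRouen) with t on 7 df. Apply the same variance rule to the secondary GEE models, and state which link and response each binary secondary endpoint uses. Recheck the 93% power under the chosen model with the assumed ICC written down.

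The change takes a few sentences and no new data. The cost is wider intervals (critical value 2.36 instead of 1.96) and lower power. Simulated power at 33%, going from uncorrected z to K−1 with t on 7 df:

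| Assumed ICC | Offset model | Identity model |
|---|---|---|
| 0.04 | 97% to 92% | 95% to 86% |
| 0.05 | 95% to 87% | 91% to 78% |
| 0.10 | 77% to 62% | 67% to 46% |

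This loss comes from the small-sample correction, not from repairing the link.

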Preliminary data: D-CLIP [clinicaltrials.gov #NCT01283308, Emory University and Madras Diabetes Research Foundation (MDRF) investigators] is an on-going, translational, diabetes prevention study comparing standard lifestyle advice to a step-wise, culturally tailored program (group lifestyle classes plus metformin for participants not responding to lifestyle change alone) among 602 people with prediabetes in India.²⁵ D-CLIP was developed based on the DPP Curriculum.^{79,80} Early unpublished D-CLIP results are promising. The participation rate for intervention classes was high (83%), and loss to follow-up was low (9%). At eighteen months, lifestyle participants had significantly greater reductions in weight (-1.7 vs. -0.8 kg), BMI (-0.6 vs. -0.3 kg/m²), and waist circumference (-2.7 vs. -2.0 cm) than controls. Additionally, intervention participants showed greater improvements in systolic blood pressure, triglycerides, and HbA_{1c}; 21% of controls achieved improvement in two or more of these risk factors while 33% of intervention group did so. Similar to previous studies showing that weight, BMI, and waist circumference reductions significantly predicted diabetes risk reduction in lifestyle interventions,⁸¹ preliminary D-CLIP analyses show a 51% relative risk reduction in diabetes incidence in intervention participants compared to controls. The effects of the D-CLIP intervention were consistent across sex, age, income, education, and baseline BMI and glucose intolerance.⁸²

Recommendations for improving the Indian diet to better prevent diabetes and reduce cardiometabolic risk factors will be developed based on the work assessing the value of improving food quality of the Global Nutrition and Epidemiologic Transition (GNET) initiative at Harvard University and MDRF. For example, a small crossover trial of substituting brown rice for white rice for five days, found that brown rice lowered glucose levels by 19.8% and fasting insulin by 57%.⁴⁰ GNET studies in other populations further support benefits of improving carbohydrate quality.³⁸ Moreover, studies of acceptability of brown rice in India indicate that well-informed, sensory trained panelists readily accepted brown rice,³² but translating this intervention to the public

Figure 2: Components of the Lifestyle Intervention at the Individual and Worksite Environment Levels

will require additional education and training.²⁷

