Glycemic control (HbA _{1c})	Identify eligible participants and assess improvement	X	X	X	X
Glycemic status (venous fasting plasma glucose)	Assess effects of program on glycemic status		X	X	X
Height and weight (stadiometer; weighing scale)	Baseline and changes in weight (kg), BMI (kg/m ²) and percent overweight/obese	X	X	X	X
Waist circumference (non-elastic tape measure)	Baseline and change in waist circumference	X	X	X	X
Blood pressure (automated blood pressure machine)	Baseline and change in blood pressure and hypertension	X	X	X	X
Lipid profile (fasting venous triglycerides, HDL, LDL)	Baseline and change in plasma triglycerides, LDL-cholesterol, and HDL-cholesterol	X	X	X	X
Measures of Program Cost					
Cost questionnaire (SQ)	Participant cost of diabetes care and medicines for diabetes, blood pressure, and lipids, prevention, and complications		X	X	X
Program costs (data collection from worksite, study records)	Cost (monetary, person time, etc.) of delivering program			X	X
Worksite productivity (worksite records)	Absenteeism, presenteeism, productivity, turn-over		X	X	X
Program Fidelity and Acceptability					
Weekly checklists for health educators	Checklists of required and optional activities for health educators to fill out weekly		X	X	
Participation in lifestyle intervention (attendance records, number of diet/activity records turned in)	Program attendance and adherence		X	X	
Participant feed back (SQ)	Acceptability of program components and suggestions for improvement			X	X

S = Screening; B = Baseline; A = Annually throughout follow-up period; FU = End of follow-up; SQ = study questionnaire; HbA_{1c} = glycosylated hemoglobin; BMI = body mass index; LDL = low-density lipoprotein; HDL = high-density lipoprotein

Data Analysis

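### Continuous secondary markers are analysed as raw pre-post change and called intervention effects, with no reference for the change expected without the programme

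*Combined protocol and SAP*

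**What the plan says.** The design is pre-post with no control group (Approach). Under Data Analysis, Aim 2, the primary endpoint is the indicator of meeting two or more risk-factor goals, "minus the expected probability of this endpoint in the absence of an intervention, to be taken as 21% as observed in the D-CLIP" control group. The test is on the intercept: "the p-value associated with the model's intercept will provide a measure of the statistical significance of the findings".

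For the other endpoints the section says: "A similar GEE approach will be used to estimate and test the significance of intervention effects on secondary endpoints". For continuous markers, with systolic pressure and HbA1c as examples, "the post- to pre- within-participant difference will serve as the dependent variable in a GEE model as above, with the identity link function". No expected change without the programme is named for any of them. Anthropometry, lipids and fasting glucose are secondary outcomes under Aim 2 in Specific Aims.

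The Preliminary data paragraph reports that D-CLIP lifestyle participants had "greater reductions in weight (-1.7 vs. -0.8 kg") and, after the BMI figures (-0.6 against -0.3 kg/m²), "waist circumference (-2.7 vs. -2.0 cm) than controls", all at 18 months. Sample Size Selection states the continuous targets as plain decreases: "90% power or more to detect a decrease of 2mmHg or greater in systolic blood pressure", and 95% power for an HbA1c decrease of 0.14%. For diabetes incidence the same paragraph does name a comparator, 0.07 per year.

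**The concern.** With an identity link, no covariates and nothing subtracted, the model intercept is the mean raw change. Its p-value answers whether participants changed, not whether the programme changed them. In a single-arm study those differ by whatever would have happened anyway: secular trend, ageing, being told one's results at screening, usual care.

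The plan accepts this for its primary endpoint, where it does not treat zero as the no-intervention value. It does not carry the principle to the continuous markers, although its own reference group shows that weight, BMI and waist can fall without the full programme. A reader of the final report could take a significant fall in any of these as a programme effect of that size.

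**Working it through.** **1. The plan's own figures.** The stated power for systolic pressure and HbA1c cannot be reproduced: no SD of change is given, and the annotation printed beside both (p=0.10, IIS) is undefined. They can only be back-solved. With 8 × 250 = 2,000 enrolled and 20% lost, 1,600 remain, 200 per site. A two-sided 5% level is assumed, since sidedness is not stated. For a one-sample test against zero,

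implied SD = target × √n_eff / (1.96 + z_power), with n_eff = 1,600 / (1 + 199 × ICC).

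| ICC | n_eff | SBP: 2 mmHg, 90% | HbA1c: 0.14%, 95% |
|---|---|---|---|
| 0 | 1,600 | 24.7 mmHg | 1.55% |
| 0.02 | 321.3 | 11.1 mmHg | 0.70% |
| 0.05 | 146.1 | 7.5 mmHg | 0.47% |
| 0.10 | 76.6 | 5.4 mmHg | 0.34% |

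The text does not say whether these targets are raw or net of background.

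**2. Control change as a share of lifestyle-arm change (Preliminary data).**

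| Marker | Lifestyle | Control | Control / lifestyle | Difference |
|---|---|---|---|---|
| Weight, kg | -1.7 | -0.8 | 0.8/1.7 = 47% | -0.9 |
| BMI, kg/m² | -0.6 | -0.3 | 0.3/0.6 = 50% | -0.3 |
| Waist, cm | -2.7 | -2.0 | 2.0/2.7 = 74% | -0.7 |

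**3. How often the zero test would call an equivalent programme effective.** Suppose participants change exactly as D-CLIP controls did. SE = SD / √n_eff; rejection probability at two-sided 5%, by the normal distribution and by the noncentral t with 7 df (8 sites). The SDs and ICCs are assumptions; neither is in the documents.

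- Weight, 0.8 kg, most to least favourable to rejection. SD 3 kg, ICC 0.01: SE = 3/√535.1 = 0.130, ratio 6.17, about 100%. SD 5 kg, ICC 0.10: SE = 5/√76.6 = 0.571, ratio 1.40, 29% (normal) or 23% (t).
- Waist, 2.0 cm. SD 5 cm, ICC 0.01: SE = 0.216, ratio 9.25, about 100%. SD 8 cm, ICC 0.10: SE = 0.914, ratio 2.19, 59% (normal) or 47% (t).
- If true background is only half the control change, the same corners give 9-87% for weight (0.4 kg) and 16% to over 99% for waist (1.0 cm).

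**4. Systolic pressure and HbA1c.** No control change is given, so only a conditional statement is possible. The stated power fixes target/SE at 1.96 + 1.28 = 3.24 for systolic pressure and 1.96 + 1.64 = 3.60 for HbA1c. If background were an improvement of 10%, 25% or 50% of the target, a programme with no effect would reach significance 6%, 13% or 37% of the time for systolic pressure and 7%, 15% or 44% for HbA1c. If untreated values would instead rise by 25% of the target, a programme with a net effect equal to the target would show only 75% of it, and power would fall to Φ(0.75 × 3.24 − 1.96) = 68% and Φ(0.75 × 3.60 − 1.96) = 77%.

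**5. Whether another part of the plan corrects this.** The marginal structural models in Aim 2 address non-adherence and loss to follow-up. The CARRS comparison, in Sustainability, Dissemination, and Future Plans, would address secular trends, but it is an additional analysis that depends on separate funding.

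**The case against.** **The zero null is inferred.** The section describes a similar approach and refers back to the primary model, so a reference may have been intended. That is a fair reading, but none is stated for any continuous marker, and the same correction is then needed.

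**D-CLIP controls were not untreated.** Sample Size Selection says they saw a physician and a dietician, attended two classes and received handouts, and expects a community control to do less well on the primary measure. This stands. A reader might infer that 47%, 50% and 74% are the shares of change due to background, or that raw change overstates the effect by the corresponding factors. The documents do not support that: these are early 18-month contrasts of full against minimal intervention, while the endpoint here is at 3 years. They show that zero is not a safe reference; they do not measure the correction. The plan nevertheless uses this same group as its no-intervention reference for the primary endpoint.

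**Bias need not be upward for every marker.** This stands too. For systolic pressure, triglycerides and HbA1c the Preliminary data say only that the intervention group improved more. The assumed incidence of 0.07 per year in prediabetes suggests that HbA1c could drift upward untreated, in which case raw change would understate benefit.

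**Regression to the mean.** Because entry requires HbA1c of 5.7% or more, one might infer that HbA1c change is inflated by selection. That holds only if the screening value serves as the pre value. Table 4 describes the test as "Identify eligible participants and assess improvement" and schedules it at screening and again at baseline; nothing says that the screening value is used. If it were, (1 − reliability) × (mean above 5.7% − overall mean) gives about 0.02-0.12% on assumed screening means of 5.5-5.7%, SDs of 0.5-0.6% and reliabilities of 0.80-0.95. This is a reason to name the visit, not a finding of bias.

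**The design is openly chosen.** The Approach section defends having no control group on the strength of earlier randomised evidence. That evidence supports lifestyle change in general; it does not turn a raw change here into an effect estimate.

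**Conclusion.** The point holds for the continuous secondary endpoints. Followed as written, the plan reports mean within-participant change, tested in effect against zero, as an intervention effect. For weight, BMI and waist its own reference group improved by about half to three quarters of the lifestyle-arm change, so the raw change cannot be credited wholly to the programme. For systolic pressure, HbA1c and lipids the background change is unknown and its sign open.

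The error rates are illustrations: 23-100% for weight and 47-100% for waist rest on 1,600 completers at 8 sites, ICC 0.01-0.10, SDs of 3-5 kg and 5-8 cm, and background equal to the D-CLIP control change. Smaller true background lowers them. The absence of a stated reference does not depend on these assumptions. The point does not extend to the primary endpoint, which has a reference.

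**What to change.** - Label the raw pre-post result for each continuous marker as within-participant change, not as an intervention effect.
- For any effect claim, compare with the D-CLIP control mean change for that marker at the closest visit: net change = trial mean change − control mean change, with variance = cluster-robust variance of the trial mean + variance of the control mean. This follows the principle already used for the primary endpoint.
- Restrict that comparison to participants with prediabetes, or show it separately for them. D-CLIP enrolled only people with prediabetes, while about one third here are expected to have unmedicated diabetes (Sample Size Selection assumes 2/3 with prediabetes).
- State beside the result that the reference group had a minimal intervention and came from a different, single-site clinic setting. The contrast is an externally referenced estimate, not a randomised effect.
- Name the baseline visit in Table 4, not screening, as the source of the pre value.
- State whether the 2 mmHg and 0.14% targets are raw or net, and give the SD, the ICC and the meaning of the p=0.10, IIS annotation.

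The cost is analysis-plan wording and obtaining D-CLIP control means and variances; D-CLIP investigators belong to two of the partner institutions. The downside is smaller estimates where controls also improved, and wider intervals throughout.
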